### Treatment Arms and Duration:

- Part 1: a monotherapy dose escalation of BMS-986277.
  - Four dose levels:  $3 \times 10^{10}$  viral particles (vp),  $3 \times 10^{11}$  vp,  $1 \times 10^{12}$  vp, and  $3 \times 10^{12}$  vp.
  - 6-week DLT evaluation period to assess safety with multiple injections which may be extended due to dose delays.
  - Dosing for the initial participants into each cohort in Part 1 will be staggered by 7 days to monitor for sentinel events.
  - Participants will receive 2 cycles (Cycle 1: 42 days, Cycle 2: 28 days) of BMS-986277.
- Part 2: a combination dose escalation of BMS-986277 (using the RD from Part 1; up to 2 cycles) in combination with nivolumab (480 mg Q4W; up to 26 cycles).
  - Participants will receive BMS-986277 at the BLRM-RD, or a lower dose than the BLRM-RD from Part 1.
    - ◆ Dosing for the initial participants into each cohort will be staggered by 7 days to monitor for sentinel events.
- Part 3: a 3-cohort expansion.
  - In Cohort 1, participants with low CD8 TILs ( $CD8 < 2\%$ ) will be treated with BMS-986277 (using the RD from Part 2; up to 2 cycles) in combination with nivolumab (480 mg Q4W; up to 26 cycles).
  - In Cohort 2, participants with mid CD8 TILs ( $2\% \leq CD8 < 20\%$ ) will be treated with BMS-986277 (using the RD from Part 2; up to 2 cycles) in combination with nivolumab (480 mg Q4W; up to 26 cycles).
  - In Cohort 3, participants with high CD8 TILs ( $\geq 20\%$ ) will be treated with BMS-986277 monotherapy (using the RD from Part 1; up to 2 cycles) with an option for subsequent nivolumab treatment (480 mg Q4W; up to 26 cycles).

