#### 7.1.3.1 BMS-986277 Infusion (Part 1)

In Part 1 (monotherapy dose escalation), four dose levels of BMS-986277 ( $3 \times 10^{10}$  vp,  $3 \times 10^{11}$  vp,  $1 \times 10^{12}$  vp, and  $3 \times 10^{12}$  vp) are planned. Eligible participants will receive an IV infusion of BMS-986277 at the assigned dose, starting at time zero administered directly into the venous access point using a syringe pump on Days 1, 15, 17, and 19 on Cycle 1 and on Days 1, 3, and 5 on Cycle 2. BMS-986277 will be administered over 5 minutes except for the  $3 \times 10^{12}$  vp dose, which will be administered over 15 minutes. Participants will receive a maximum of 2 cycles of treatment (see [Section 7.1.1](#)).

On BMS-986277 dosing days, participants will receive antipyretic prophylaxis predose and postdose (see [Section 7.7.2](#)). This will generally be acetaminophen/paracetamol and/or ibuprofen at a dose and schedule to manage the participant's clinical condition, providing that it follows the prescribing information for the product(s). Other medications, including diphenhydramine and

indomethacin may be used in line with the study site’s standard practice providing they are not excluded concomitant medications (see [Section 7.7.1](#)). Corticosteroid use may be considered under certain circumstances but should be discussed with the Medical Monitor (or designee) prior to initiation.

At the end of the infusion the administration line should be flushed with normal saline to ensure that the full viral dose has been administered. This flush should only use a sufficient amount of saline to flush the line and should not exceed 30 mL.

Participants can receive prophylactic IV hydration after the end of each infusion, unless clinically contraindicated (see [Section 7.7.2](#)). Up to 1 L of normal saline may be administered over 4 hours, adjusted to meet the physiological and clinical requirements of the individual participant (eg, participant body mass index [BMI], concurrent conditions).

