#### 3 STUDY DESCRIPTION

## 3.1 Study Design

This is a Phase 1/2a, multicenter, open-label, non-randomized study of CD80/ $\alpha$ CD3 Oncolytic Virus (BMS-986277) alone and in combination with nivolumab for the treatment of metastatic or advanced epithelial tumors in male and female participants. There will be up to 4 sequential IV dose panels of BMS-986277 in monotherapy and 2 sequential IV dose panels of BMS-986277 in combination with nivolumab (480 mg Q4W).

The study will be conducted in 3 Parts:

- Part 1: a single agent monotherapy dose escalation of BMS-986277
  - Four dose levels:  $3 \times 10^{10}$  vp,  $3 \times 10^{11}$  vp,  $1 \times 10^{12}$  vp, and  $3 \times 10^{12}$  vp.
  - 6 week dose limiting toxicity (DLT) period to assess safety with multiple injections.
  - Dosing for the initial participants into each cohort in Part 1 will be staggered by 7 days to monitor for sentinel events
  - Participants will receive 3 cycles (28 day cycles; up to 6 max) of BMS-986277.
  - This part will determine the recommended dose to administer in the combination dose escalation (Part 2), based on the Bayesian Logistic Regression Model Recommended Dose (BLRM-RD) and overall clinical assessment of all available safety, pharmacokinetics (PK), pharmacodynamics, and efficacy data.
- Part 2: a combination dose escalation of BMS-986277 in combination with nivolumab in participants with low or mid CD8 tumor infiltrating lymphocytes (TILs) only
  - Participants will receive BMS-986277 at the BLRM-RD, or a lower dose than the BLRM-RD from Part 1.
  - Dosing for the initial participants into each cohort will be staggered by 7 days to monitor for sentinel events
  - BMS-986277 will be administered for up to three 28-day cycles, and nivolumab will be administered at 480mg Q4W for up to 26 cycles.
  - Low CD8 TILs are defined as CD8 < 2%

  - Mid CD8 TILs are defined as  $2\% \le CD8 \le 20\%$

- This part will determine the recommended Phase 2 dose (RP2D) based on the recommendations from the BLRM-copula and overall clinical assessment of all available safety, PK/pharmacodynamic, and efficacy data.
- Part 3: a 2 cohort dose expansion phase of BMS-986277 in combination with nivolumab in participants with low or mid CD8 tumor infiltrating lymphocytes (TILs) only
  - Participants will receive BMS-986277 at the RP2D established in Part 2 for up to 3 cycles, and nivolumab will be administered at 480mg Q4W for up to 26 cycles.

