# 7.2.1 Monotherapy Dose Escalation (Part 1)

In the monotherapy dose escalation part of the study, participants will receive BMS-986277 at one of the four planned dose levels (3 x  $10^{10}$ , 3 x  $10^{11}$ , 1 x  $10^{12}$ , or 3 x  $10^{12}$  vp). At each dose level BMS-986277 will be administered as a single IV infusion (D1) before proceeding to a single dosing cycle (3 doses, Days 15, 17, and 19). Participants who complete the first cycle without a

DLT, who have no clinical evidence of disease progression, and are considered suitable for further treatment may receive up to two more cycles of BMS-986277. Optional treatment up to 6 cycles if deemed safe and after risk/benefit evaluation and approval by Medical Monitor (or designee) are permitted.

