# 8.4.1 Study Therapy

#### **Summary:**

Unless otherwise specified, administration of study therapy will be summarized separately for BMS-986277 and nivolumab and presented by dose level and biomarker level; tabulations by part, cohort, and indications may also be performed, as appropriate.

• Number (%) of treated participants exposed for specified periods of time such as:

- **Part 1**: less than 2 weeks (lead-in period only), 2 weeks to 6 weeks (1 cycle), 6weeks to 14 weeks (up to 3 cycles), and more than 14 weeks (up to 6 cycles).
- Parts 2 and 3: less than 2 weeks (sequential dosing of BMS-986277 prior to nivolumab),
   2 weeks to 4 weeks (1 combination cycle), 4 weeks to 12 weeks (up to 3 cycles), and more than 12 weeks (nivolumab maintenance).
- For this analysis, the exposure period is defined as first dose of either study drug to last dose of either study drug and will be summarized as a treatment regimen (rather than separately).

Descriptive statistics will be provided for the following:

- Number of doses
- Duration of therapy
- Cumulative dose
- Relative dose intensity (RDI)
  - Categories: < 50%; 50 < 70%; 70 < 90%; 90 < 110%;  $\ge 110\%$

Details for the calculations of these parameters are presented in Table 6 and Table 7.

Table 6: Study Therapy Parameter Definition for Part 1

Parameter	BMS-986277	
Dosing Schedule per Protocol	Cycle 1: 2 week lead-in period followed by 4 week sequential dosing period	
	Cycles 2-6: sequential dosing every 4 weeks	
	If only 1 dose is administered: Duration of therapy (weeks) = 2 weeks	
Duration of Therapy	If more than 1 dose is administered: Duration of therapy (weeks) = (last dose date - first dose date + 24) / 7	
	(Note: 24 days is the time between Day 19 and Day 43)	
Dose	Dose (vp) is defined as total dose administered in vp/dose at each dosing date as collected on the CRF.	
Cumulative Dose	Cum dose (vp) is sum of the doses (vp) administered to a participant.	
	If only 1 dose is administered: RDI (%) = [cumulative dose (vp) / (planned* dose (vp)] x 100	
Relative Dose Intensity	If more than 1 dose is administered: RDI (%) = {cumulative dose (vp) / [(duration of therapy (weeks) x {planned* dose (vp) + 3 x number of cycles x planned* dose (vp)}) / (2 weeks + number of cycles x 4 weeks)]} x 100	

\*Planned dose is the assigned dose recorded on the CRF.

Parameter	BMS-986277	Nivolumab

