Dosing Schedule per Protocol	Sequential dosing on Days 1, 3, and 5 in a 28 day cycle for up to 3 cycles	480 mg on Day 15 in a 28 day cycle for up to 26 cycles
Duration of Therapy	Duration of therapy (weeks) = (last dose date of BMS-986277 - first dose date of BMS-986277 + 24) / 7 (Note: 24 days is the time between Day 5 and Day 29)	Duration of therapy (weeks) = (last dose date of nivolumab - first dose date of nivolumab + 28) / 7
Dose	Dose (vp) is defined as total dose administered in vp/dose at each dosing date as collected on the CRF.	Dose (mg) is defined as total dose administered in mg at each dosing date as collected on the CRF.
Cumulative Dose	Cum dose (vp) is sum of the doses (vp) administered to a participant.	Cum dose (mg) is sum of the doses (mg) administered to a participant.
Relative Dose Intensity	RDI (%) = {cumulative dose (vp) / [(duration of therapy (weeks) x 3 x number of cycles x planned* dose (vp)) / (number of cycles x 4 weeks)]} x 100	RDI (%) = {cumulative dose (mg) / [(duration of therapy (weeks) x number of cycles x 480 mg) / (number of cycles x 4 weeks)]} x 100

Table 7: Study Therapy Parameter Definition for Parts 2 and 3

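### The SAP is written for three cycles of BMS-986277 (up to six in Part 1) where the protocol gives two, so its exposure bands are cut and labelled for the wrong treatment course

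*SAP*

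**What the plan says.** **SAP.** Section 3.1 sets the Part 1 course: "Participants will receive 3 cycles (28 day cycles; up to 6 max) of BMS-986277". Section 7.2.1 repeats the extension: "Optional treatment up to 6 cycles if deemed safe". For Part 2, section 3.1 states "BMS-986277 will be administered for up to three 28-day cycles", and for Part 3 "Participants will receive BMS-986277 at the RP2D established in Part 2 for up to 3 cycles"; sections 7.2.2 and 7.2.3 agree. The dosing-schedule row of Table 7 reads "Sequential dosing on Days 1, 3, and 5 in a 28 day cycle for up to 3 cycles", and the matching row of Table 6 runs to Cycle 6.

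Section 8.4.1 counts participants by exposure band. The Parts 2-3 bands end with "4 weeks to 12 weeks (up to 3 cycles), and more than 12 weeks (nivolumab maintenance". In Part 1 the last two bands are 6 to 14 weeks (up to three cycles) and above 14 weeks (up to six). Exposure for this table runs from the first to the last dose of either drug.

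**Protocol.** The Synopsis says of Part 1: "Participants will receive 2 cycles (Cycle 1: 42 days, Cycle 2: 28 days) of BMS-986277". Section 7.1.3.1 adds "Participants will receive a maximum of 2 cycles of treatment". Tables 7.1.4-1, 7.1.5-1 and 7.1.6-1 give up to two 28-day cycles in Part 2 and in all Part 3 cohorts. Tables 2-3 and 2-4 head the Cycle 3 and later columns as nivolumab only.

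**Versions.** The SAP revision history says that it incorporates changes up to Revised Protocol 03, and its amendment table stops at Amendment 04. The protocol's document history dates the two-cycle limit to Revised Protocol 05, 18-May-2018.

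**The concern.** The two documents describe different courses of the investigational product, and the SAP turns its version into an analysis rule. The upper edges of its bands are the ends of a three-cycle course. For anyone treated under the two-cycle text, those edges no longer separate time on the combination from time on nivolumab alone.

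At stake is whether the exposure table in the study report can be read correctly. It would group participants who stopped after two combination cycles with participants who went on to nivolumab alone, under a label tied to a three-cycle course. In Part 1 it would carry a band that the described course cannot reach. The regimen descriptions in SAP 3.1 and 7.2, if carried into the report, would also misstate the treatment.

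**Working it through.** **Inputs.** Part 1 dosing: Cycle 1 Days 1, 15, 17 and 19, then Days 1, 3 and 5 of Cycle 2, with Cycle 1 lasting 42 days (protocol Table 7.1.3-1 and Synopsis). Parts 2-3 (Cohorts 1-2): BMS-986277 on Days 1, 3 and 5 of a 28-day cycle, nivolumab on Day 15 (Tables 7.1.4-1 and 7.1.5-1). Exposure = (last dose day - first dose day)/7 on nominal days.

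**1. Reproduce the SAP's band edges.**
- Parts 2-3: 4 weeks x 3 cycles = 12 weeks.
- Part 1: 2-week lead-in + 4 weeks x 3 cycles = 14 weeks.

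Both match, so the edges come from the three-cycle limit. With two cycles the same formulas give 4 x 2 = 8 and 2 + 4 x 2 = 10 weeks.

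**2. Place Parts 2-3 participants in the SAP's bands.**

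| Last dose | Study day | Exposure (weeks) | SAP band (weeks) | BMS-986277 cycles, SAP | BMS-986277 cycles, protocol |
|---|---|---|---|---|---|
| C2D15 | 28 + 15 = 43 | 42/7 = 6.0 | 4 to 12 | 2 | 2 |
| C3D15 | 56 + 15 = 71 | 70/7 = 10.0 | 4 to 12 | 3 | 2 |
| C4D15 | 84 + 15 = 99 | 98/7 = 14.0 | above 12 | 3 | 2 |

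Under the SAP's limit the bands are consistent: C4D15 is the first nivolumab-only dose and falls above 12 weeks. Under the protocol text the first nivolumab-only dose is C3D15, and it falls in the band below. Weeks 8 to 12, which are 4 of that band's 8 weeks, are nivolumab only. The ±3-day nivolumab window puts C3D15 on Days 68 to 74, or 9.6 to 10.4 weeks, so the band does not change.

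**3. Place a full Part 1 course.** Cycle 2 starts on Day 43, so its third dose is on Day 47: (47 - 1)/7 = 6.6 weeks. Reaching 14 weeks (98 days) would take 98 - 46 = 52 days of accumulated delay. On the nominal schedule the band above 14 weeks is therefore empty. Under the SAP's limits, four cycles end on Day 103 (14.6 weeks) and six on Day 159 (22.6 weeks), which is what the band was meant to hold.

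**4. Check the formulas in Tables 6 and 7.**
- Table 6, two full cycles: duration = (47 - 1 + 24)/7 = 10 weeks. Planned doses are 1 + 3 x 2 = 7 over 2 + 2 x 4 = 10 weeks, so relative dose intensity = 7/[(10 x 7)/10] = 100%.
- Table 7, BMS-986277, two full cycles: the last dose is on Day 33, duration = (33 - 1 + 24)/7 = 8 weeks, and relative dose intensity = 6/[(8 x 6)/8] = 100%.

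The formulas use the participant's own number of cycles and still work. Only the dosing-schedule rows are out of date.

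**The case against.** The best defence is that this is declared version lag with little consequence. The SAP names the protocol version it rests on, and the protocol says that the SAP will be finalized before the final database lock. The bands are offered as examples, and SAP 8.1 leaves grouping schemes to the data presentation plan. The same section summarizes number of doses, duration and cumulative dose separately for each drug, so a maximum of six BMS-986277 doses in Parts 2-3 would be visible. All of that stands, and it limits the size of the point. It does not remove it: SAP section 1 waives an amendment only for protocol changes with no impact on the analysis methodology, and this change affects the stated bands and regimen definitions.

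A reader might infer two stronger claims that the documents do not support.

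- *That the table would report a third combination cycle nobody received.* The 4-to-12-week label says up to three cycles without the word combination, a nivolumab-only Cycle 3 does exist in the protocol, and no document says how many cycles anyone received.
- *That adverse-event summaries by dose level are distorted because early, low-dose participants had more cycles.* The permitted maximum in Part 1 does differ: 7 doses for two cycles, 10 for three, 19 for six. But no first-dose date is given, nor any count treated before Revised Protocol 05. The SAP places first dosing after the change made on 11-Dec-2017. Nineteen doses end on Day 159, which from that date is 18-May-2018, the issue date of Revised Protocol 05, with no delay allowed. Participants may also be added later at any dose level, so the lower doses need not hold the earlier participants. Different limits within Part 1 are a possibility, not a finding. An added table restricted to the period through Cycle 2 would not give a common window either, since Cycle 2 depends on no DLT, no clinical progression and suitability for further treatment.

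**Conclusion.** The contradiction is established, and in this form the point holds. SAP 3.1, 7.2.1-7.2.3, 8.4.1 and the dosing-schedule rows of Tables 6 and 7 use three cycles (six in Part 1); the protocol uses two throughout. The consequence is misclassification in one descriptive table. In Parts 2-3 it affects, on the nominal schedule, participants under the two-cycle text whose last dose is nivolumab on C3D15; their number cannot be known from the documents. In Part 1 it leaves an empty top band.

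The duration and relative-dose-intensity formulas are unaffected. So are the dose-escalation decisions, because the BLRM uses data from the DLT period only, and the sample size. The result assumes nominal dosing days, apart from the nivolumab window tested above. Part 3 Cohort 3, which SAP v1.0 does not describe, is outside this calculation.

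**What to change.** 1. Reconcile the BMS-986277 cycle limit between the protocol and SAP 3.1, 7.2.1-7.2.3, 8.4.1 and the dosing-schedule rows of Tables 6 and 7. Which limit applies is for the sponsor to state.
2. Re-cut and relabel the 8.4.1 bands to the reconciled limit, keeping the SAP's first-to-last-dose definition. Under the current protocol text, the Parts 2-3 edge for nivolumab only would be 8 weeks, which separates C2D15 (6.0 weeks) from C3D15 (10.0 weeks). In Part 1 a full course spans about 6.6 weeks, so no band beyond that is needed except for delays. A 10-week edge there would again leave an empty top band, because the first-to-last-dose span omits the days after the final infusion.
3. Bring the SAP's revision history and amendment table up to the protocol version that it then follows.

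The cost is SAP amendment text and revised labels in one table. No new data or additional analysis is needed.

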# Prospective biomarkers to be enrolled in Parts 2 and 3:

Low:  $CD8 < 2\% \overline{OR}$  Mid:  $2\% \le CD8 < 20\%$ 

BLRM = Bayesian Logistic Regression Model Recommended Dose; D = day; IV = intravenous; N = number; PD-L1 = PD1 ligand; Q4W = every 4 weeks; RD = recommended dose; RP2D = recommended phase two dose; TIL = tumor-infiltrating lymphocytes; VP = viral particles.

<sup>aOptional Treatment up to 6 cycles if deemed safe and after risk/benefit evaluation with Medical Monitor (or designee) approval.

# 3.2 Treatment Assignment

All enrolled participants, including those not dosed, will be assigned a participant number. Treatment group and dose level assignments will be performed using an Interactive Response Technology (IRT). The participant will be assigned to one of the following:

- Assigned to Part 1 and the assigned dose level in the monotherapy dose escalation portion of the study
- Assigned to Part 2 and the assigned dose level in the combination dose escalation portion of the study
- Assigned to Part 3 and which biomarker category in the cohort expansion portion of the study
  - There should be a minimum of 5 participants per each indication in each cohort.

Participants may be replaced in the same part and dose level under certain conditions, such as not being evaluable for the DLT period or having unevaluable tumor tissue to determine CD8 level.

# 3.3 Blinding and Unblinding

Not applicable. This is an open label study.

#### 3.4 Protocol Amendments

Table 1 lists the protocol amendments and administrative letters and only highlights the changes which affect the analysis.

Table 1: List of Protocol Amendments and Administrative Letters

Document	Date	Summary of Major Changes
Amendment 01	27-Sep-2017	Does not affect analyses.
Amendment 02	24-Oct-2017	Does not affect analyses.
Administrative Letter 01	07-Nov-2017	Does not affect analyses.
Administrative Letter 02	11-Dec-2017	Modifies the dosing window, this change occurred before any participants were dosed on this study.
Amendment 03	15-Dec-2017	Updates to the following sections: schedule of activities (including safety labs, biomarker samples, pharmacokinetic samples, and shedding samples), exploratory objectives, inclusion/exclusion criteria
Amendment 04	02-Mar-2018	Does not affect analyses.

# 3.5 Blinded Independent Central Review

Images will be submitted to an imaging core lab for all participants. Images from participants in Part 2 and 3 may be reviewed by a Blinded Independent Central Review (BICR), in addition to the investigator. Images in Part 1 will be read locally, but may be read at a later date, or at any time during the study by the BICR.

The participants' best overall response (BOR), duration of response (DOR), and progression-free survival (PFS) will be assessed using the RECIST Version 1.1 criteria (Protocol Appendix 7),

modified Response Evaluation Criteria in Solid Tumors for Immunotherapeutics (iRECIST) Version 1, and/or prostate cancer working group 3 (PCWG3, Protocol Appendix 8).

Details of the BICR responsibilities and procedures will be specified in the BICR charter.

[figure not shown]
# 4 OBJECTIVES

The objectives and endpoints for this study are shown in the following table.

**Table 2:** Objectives and Endpoints

	Objectives		Endpoints
Pri	imary		
•	To characterize the safety and tolerability of BMS-986277 administered alone and in combination with programmed death receptor 1 (PD-1) inhibitor, nivolumab, in advanced epithelial tumors.	•	Incidence of AEs, SAEs, AEs meeting protocol-defined DLT criteria, AEs leading to discontinuation, and AEs resulting in death
•	To determine the recommended dose (RD) and recommended Phase 2 dose (RP2D) and dosing schedule of BMS-986277 administered alone (RD) and in combination with nivolumab (RP2D) in participants with advanced epithelial tumors	•	Incidence of clinical laboratory test abnormalities  Vital sign abnormalities or other safety biomarkers
Sec	condary		
•	To explore the preliminary anti-tumor activity of BMS-986277 in combination with nivolumab in participants with advanced epithelial tumors (RECIST 1.1 and PCWG3)	•	ORR, DCR, mDOR, mPFS, and PFSR at 8, 16, 24 weeks depending on indication
•	To assess the pharmacokinetics and immunogenicity of BMS-986277 in blood following monotherapy or combination treatment	•	Summary measures of PK and IMG parameters of BMS-986277
		I	

Table 2: Objectives and Endpoints

AEs = adverse events; DCR = disease control rate; IMG = immunogenicity; mDOR = median duration of response; mPFS = median progression-free survival; mOS = median overall survival; ORR = objective response rate; OSR = overall survival rate; PCWG = Prostate Cancer Working Group; PFSR = progression-free survival rate; PK = pharmacokinetics; RECIST = Response Evaluation Criteria in Solid Tumors; SAEs = serious adverse events.

